#### 10.4.4.2. Laboratory Tests

Laboratory values will be summarized by treatment group, including changes and percent changes from baseline at each time point. Analyses will also be performed for each laboratory parameter by treatment group for incidence rates of both potentially clinical significant (PCS)/clinically significant (CS) values for subjects without PCS/CS value at baseline.

Numerical values of laboratory parameters from different local laboratories with different units and normal ranges will be converted to the conventional units and normalized to a standard set of reference/normal ranges. The normalization process will be performed and separated by each of the laboratory parameters. A shift analysis by normal range will be done which counts the number of patients with a low, normal or high value at baseline and a low, normal or high value post baseline.

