6.4.8.2. Laboratory Tests

Laboratory values will be summarized by treatment group, including the observed value, changes and percent changes from baseline at each time point.

A shift analysis using the normal range (except for eGFR and HbA1c) will be done which counts the number of subjects with a low, normal or high value at baseline and a low, normal or high value post baseline.

The following ranges will be used for eGFR and HbA1c

- For eGFR, the categories will be Severe = <30 mL/min/1.73m²; Moderate = ≥ 30 to <60 mL/min/1.73m²; Mild = ≥ 60 to <90 mL/min/1.73m²; and Normal = ≥ 90 mL/min/1.73m².
- For HbA1c, the categories will be $\leq 5.6\%$, $\geq 5.7\%$ to $\leq 6.4\%$, and $\geq 6.5\%$.

The baseline and worst post-baseline value will be utilized for the shift tables. Note that the shift table dealing with the fasting glucose parameter will require the lab sample to be taken while fasting. Samples taken while the subject was not fasting will not be analyzed.

The number and percentage of subjects with potentially clinically significant (PCS) laboratory values and clinically significant (CS) laboratory values (refer to [Appendix 4](#) for the criteria) will be summarized by treatment group. Hemoglobin A1c criteria is explicitly stated in Appendix 4. All other PCS and CS criteria are met when both of the following occur:

- Post-baseline values meet the thresholds listed in Appendix 4
- Baseline values or any prior post-baseline values do not meet the thresholds listed in Appendix 4

PCS chemistry laboratory values will also be classified as follows:

- Abnormal baseline:
 - Non HbA1c: >1 and $\leq 3x$ ULN at baseline and >1 and $\leq 3x$ ULN at final visit
 - HbA1c: $\geq 6.5\%$ at baseline and $\geq 6.5\%$ and $\geq 0.5\%$ change from baseline at final visit
- Elevated further:
 - Non HbA1c: >1 and $\leq 3x$ ULN at baseline or post baseline and becoming $> 3x$ ULN post baseline
- Final visit:
 - Non HbA1c: >1 and $\leq 3x$ ULN at final visit only but not at baseline or previous visits
 - HbA1c: $\geq 6.5\%$ and $\geq 0.5\%$ change from baseline at final visit only but not at baseline or previous visits
- Persistently elevated:
 - Non HbA1c: >1 and $\leq 3x$ ULN at a post baseline visit and remains >1 and $\leq 3x$ ULN until final visit
 - HbA1c: $\geq 6.5\%$ and $\geq 0.5\%$ change from baseline at a post baseline visit and remains $\geq 6.5\%$ and $\geq 0.5\%$ change from baseline until final visit
- Resolved:

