- Non HbA1c: >1 and ≤ 3 x ULN at baseline or post baseline, resolved to $<$ ULN at any post baseline visit, and remaining $<$ ULN at final visit
- HbA1c: $\geq 6.5\%$ at baseline or $\geq 6.5\%$ and $\geq 0.5\%$ change from baseline for post-baseline, resolved to $<6.5\%$ and $<0.5\%$ change from baseline at any post baseline visit, and remaining $<6.5\%$ and $<0.5\%$ change from baseline at final visit

Separate listings of all subjects with PCS and CS laboratory values will be presented. Subjects will appear once per lab parameter but may appear under multiple lab parameters. The worst post-baseline value will be utilized in the analyses.

The number and percentage of subjects satisfying Hy's Law will also be tabulated by treatment group based on the following lab findings:

- Any elevated post-baseline aminotransferases defined as:
 - ALT > 3 x ULN or
 - AST > 3 x ULN
- Elevated post-baseline serum total bilirubin (TBL) > 2 x ULN and serum alkaline phosphatase (ALP) levels < 2 x ULN

Subjects must meet all of the criteria listed above at the same time point and have normal lab parameters (ALT, AST, TBL) at baseline to be considered a Hy's Law case.

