 2. The remaining missing values with a monotone missing data pattern will be imputed in this step. Control-based PMM imputation will be performed. With this imputation model, the missing efficacy measurements in the inclisiran group will not be constructed from the observed data in the inclisiran group but rather from the observed data in the placebo group. We will also use this model to impute missing efficacy measurements in the placebo group. The MNAR statement in SAS PROC MI will be used to impute missing values under the aforementioned assumptions. This will be performed for the 100 datasets. After this step, the 100 datasets will be fully imputed.
 3. A total of 100 fully imputed datasets will be created (M=100). Since multiple imputation is a stochastic method, slight differences in output can be expected for different initial states of the random number generator. The seed numbers will be identified in the SAS programs to allow for reproducibility.

4. After the missing data imputation is completed using the above steps, absolute change/percentage change values will be calculated in each of the imputed datasets at each visit.
5. These 100 datasets will be analyzed using the MMRM described in [Appendix 1](#) for the co-primary efficacy endpoints and key secondary efficacy endpoints.
6. Treatment effects (difference in LS means between treatments) from these 100 analyses will then be combined using Rubin's Method via SAS PROC MIANALYZE procedure for each endpoint.

APPENDIX 4. CRITERIA FOR POTENTIALLY CLINICALLY SIGNIFICANT AND CLINICALLY SIGNIFICANT ABNORMAL LABORATORY TESTS

Hemoglobin A1C criteria is explicitly stated in the table below.

All other criteria are met when both of the following occur:

- Post-baseline values meet the thresholds below
- Baseline values or any previous post-baseline values do not meet the thresholds below

Parameter	Unit	Lower Boundary	Upper Boundary
Hematology			
Hematocrit	%	$\leq 0.8 \times \text{LLN}$	N/A
Hemoglobin	g/dL	$\leq 10 \text{ g/dL}$	N/A
Platelet Count	$10^9/\text{L}$	$\leq 75^*$	$\geq 700^*$
White Blood Cell Count	$10^9/\text{L}$	≤ 2.8	≥ 16
Serum Chemistry			
Alanine Aminotransferase (ALT/SGPT)	U/L	N/A	$>1 \text{ and } \leq 3 \times \text{ULN}$
Alanine Aminotransferase (ALT/SGPT)	U/L	N/A	$>3 \text{ and } \leq 5 \times \text{ULN}^*$
Alanine Aminotransferase (ALT/SGPT)	U/L	N/A	$>5 \text{ and } \leq 10 \times \text{ULN}^*$

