Alanine Aminotransferase (ALT/SGPT)	U/L	N/A	$>10 \text{ and } \leq 20 \times \text{ULN}^*$
Alanine Aminotransferase (ALT/SGPT)	U/L	N/A	$>20 \times \text{ULN}^*$
Alkaline Phosphatase	U/L	N/A	$>2 \times \text{ULN}^*$
Aspartate Aminotransferase (AST/SGOT)	U/L	N/A	$>1 \text{ and } \leq 3 \times \text{ULN}$
Aspartate Aminotransferase (AST/SGOT)	U/L	N/A	$>3 \text{ and } \leq 5 \times \text{ULN}^*$
Aspartate Aminotransferase (AST/SGOT)	U/L	N/A	$>5 \text{ and } \leq 10 \times \text{ULN}^*$
Aspartate Aminotransferase (AST/SGOT)	U/L	N/A	$>10 \text{ and } \leq 20 \times \text{ULN}^*$
Aspartate Aminotransferase (AST/SGOT)	U/L	N/A	$>20 \times \text{ULN}^*$
Creatine Kinase (CK)	U/L	N/A	$>1 \text{ and } \leq 3 \times \text{ULN}$
Creatine Kinase (CK)	U/L	N/A	$>3 \text{ and } \leq 5 \times \text{ULN}$
Creatine Kinase (CK)	U/L	N/A	$>5 \times \text{ and } \leq 10 \times \text{ULN}^*$
Creatine Kinase (CK)	U/L	N/A	$>10 \text{ and } \leq 20 \times \text{ULN}^*$
Creatine Kinase (CK)	U/L	N/A	$>20 \times \text{ULN}^*$
Hemoglobin A1C	%	N/A	$\geq 6.5\% \text{ and } \geq 0.5\% \text{ change from baseline}$
Serum Creatinine	mg/dL	N/A	$\geq 50\% \text{ increase from Baseline or } >2 \text{ mg/dL}^*$
Total Bilirubin	mg/dL	N/A	$>2 \times \text{ULN}^*$

LLN: Lower limit of the standard reference (normal) range; ULN: Upper limit of the standard reference (normal) range; N/A is Not Applicable.

*Clinically significant laboratory boundaries.

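### The SAP's laboratory PCS/CS rule adds a prior-post-baseline condition that is redundant if each value is tested in turn, and loses within-band or past-threshold rises if the worst value is selected first

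*SAP*

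**What the plan says.** Protocol 10.4.4.2 reports incidence rates of PCS and CS values "for subjects without PCS/CS value at baseline". The only restriction is on the baseline value.

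SAP 6.4.8.2 counts subjects: "The number and percentage of subjects with potentially clinically significant (PCS) laboratory values and clinically significant (CS) laboratory values". HbA1c has its own criterion. For all other parameters two conditions must hold:

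- Condition 1: "Post-baseline values meet the thresholds listed in Appendix 4".
- Condition 2: "Baseline values or any prior post-baseline values do not meet the thresholds listed in Appendix 4".

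Appendix 4 restates Condition 2: "Baseline values or any previous post-baseline values do not meet the thresholds below". It is therefore not a slip confined to one place.

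Later in 6.4.8.2, in the paragraph on listings, the SAP says: "Subjects will appear once per lab parameter but may appear under multiple lab parameters". The next sentence is: "The worst post-baseline value will be utilized in the analyses".

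In Appendix 4, ALT, AST and CK have mutually exclusive bands: above 1 to 3, above 3 to 5, above 5 to 10, above 10 to 20, and above 20 times ULN. The CS bands start above 3 times ULN for ALT and AST and above 5 times ULN for CK. Total bilirubin and ALP (above 2 times ULN) and creatinine (a rise of at least 50% from baseline, or above 2 mg/dL) have a single limit with no upper end.

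SAP section 8 records that the identification of PCS and CS values was changed from the protocol. It does not say how or why.

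**The concern.** Condition 2 does two jobs. It removes subjects who were already abnormal at baseline, as the protocol intends. It also disqualifies a post-baseline value when an earlier post-baseline value already met the criterion. The second job sits badly with a rule that uses the worst value, because in a progressive abnormality the worst value is by nature preceded by lesser ones.

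At stake are the CS counts for liver enzymes, CK, bilirubin, ALP and creatinine. Two programmers could follow the text faithfully and produce different tables. Under one of those programs, a single spike is counted and a rise within a band over repeat dosing is not.

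**Working it through.** No sample size or power figure bears on this point. The check is to apply the two conditions to constructed records.

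**Inputs.** The conditions are from SAP 6.4.8.2, the bands and limits from Appendix 4, and the baseline-only comparator from protocol 10.4.4.2. The text leaves two things open:

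- whether each post-baseline value is tested in turn, or the worst value is selected first and only that value tested;
- whether the thresholds in Condition 2 mean the same band, or any band of that parameter.

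**Results by reading.** Baseline is normal unless stated. ALT and bilirubin are in multiples of ULN, creatinine in mg/dL. A tied worst value is taken at its first occurrence.

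| Record | Each value, same band | Worst first, same band | Each value, any band | Worst first, any band |
|---|---|---|---|---|
| ALT 4 at every visit | >3–5 | >3–5 | >3–5 | >3–5 |
| ALT 2, 4, 8, 12 | all four bands entered | >10–20 | >1–3 only | none |
| ALT 3.5 then 4.5 | >3–5 | none | >3–5 | none |
| ALT 6 then 9 | >5–10 | none | >5–10 | none |
| Bilirubin 2.2, 2.6, 3 | counted | none | counted | none |
| Creatinine 2.1, 2.3, 2.6 | counted | none | counted | none |
| Baseline ALT 1.5, later 8 | >5–10 | >5–10 | none | none |

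The ALT 3.5 then 4.5 row shows the mechanism. Tested in turn, 3.5 has no earlier qualifying value, so the subject is counted at that visit, and 4.5 merely fails to count a second time. With the worst value first, only 4.5 is examined. The earlier 3.5 lies in the same band, Condition 2 fails, and the subject appears nowhere.

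**Exhaustive check of the each-value, same-band reading.** Take five visits and six possible ALT levels, one normal and one in each of the five bands. There are 6^5 = 7,776 records. Each band is entered in 7,776 − 5^5 = 4,651 of them, which gives 5 × 4,651 = 23,255 subject-band pairs. None is lost. Creatinine with three levels at or below 2 mg/dL and three above gives 7,776 − 3^5 = 7,533 records that ever exceed 2 mg/dL. Again none is lost, so on this reading the clause is redundant.

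**The same creatinine records, worst value first.** A record is counted only if its first value above 2 mg/dL is also its maximum. With i earlier values at or below 2, and 4, 5 or 6 levels not exceeding that first value, the number counted is the sum over i = 0 to 4 of 3^i × (4^(4−i) + 5^(4−i) + 6^(4−i)) = 2,177 + 1,215 + 693 + 405 + 243 = 4,733. The number lost is 7,533 − 4,733 = 2,800. This counts hypothetical patterns with equal weight. It is not an expected rate.

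**The word *or* in Condition 2.** Read literally, it is enough that either the baseline or some earlier value fails the criterion. On that reading too, no subject with a normal baseline is lost.

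**The case against.** The strongest reply is that the SAP never says the worst value is selected before the conditions are applied. The worst-value sentence stands in the listings paragraph. It can be read as choosing which record to display, with Conditions 1 and 2 already applied value by value. On that reading nothing is lost. This stands, and it means the loss cannot be stated as what the SAP does. It does not rescue the clause, which is then redundant, and the sentence speaks of analyses rather than listings.

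A reader might go further and infer any of the following. The documents do not support them.

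- *All sustained and rising abnormalities are dropped.* Even with the worst value first, a tied flat elevation is counted at its first occurrence. A rise across ALT, AST or CK bands, tested band by band, is counted in the highest band.
- *A known share is missed.* If m untied, exchangeable values lie in one band and the worst is picked first, the worst is not the first in (m−1)/m of cases: 50% for two visits, 67% for three. That is an identity under those assumptions. The documents give no frequency for such patterns, and tested in turn the share is 0%.
- *The Persistently elevated class is largely emptied.* The chemistry classes in 6.4.8.2 have their own definitions. If Condition 2 gated them, the Abnormal baseline class, which requires a baseline value above 1 and up to 3 times ULN, would be empty. The coherent reading is that it does not gate them.
- *The safety comparison is biased toward no harm.* That needs both the worst-first reading and a drug effect of this shape. Shift tables on the worst value, the Hy's Law table and the hepatic and renal event searches do not use Condition 2.

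Those other outputs limit the harm but do not replace the CS counts. Shift tables by normal range put ALT 1.1 and 12 times ULN in the same high cell. Hy's Law needs concurrent bilirubin elevation. Elevated further and Persistently elevated are built around the range above 1 and up to 3 times ULN, so a subject going from normal to 4 and then 4.5 fits neither. The departure from the protocol is declared in SAP section 8, but without content.

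**Conclusion.** The point holds as a defect in a stated rule, not as proof that cases will be missed. SAP 6.4.8.2 and Appendix 4 carry a condition that the protocol lacks. In the records examined, it never adds a valid case.

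With each value tested in turn against the same band, it changes no subject count. With the worst value selected first, it drops subjects whose worst value follows a lower one in the same ALT, AST or CK band, or past the same bilirubin, ALP or creatinine limit. If any band of the parameter disqualifies, escalation across bands is also lost from the CS bands.

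The size of any loss is zero or unknown, depending on how the rule is programmed. The conclusion rests on the wording alone and assumes no drug effect. It concerns the reproducibility of the CS laboratory counts and does not touch the efficacy endpoints.

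**What to change.** 1. In SAP 6.4.8.2 and Appendix 4, strike the reference to prior or previous post-baseline values from the second condition. This restores the baseline-only restriction of protocol 10.4.4.2.
2. State that a subject is counted for a band or threshold if the worst post-baseline value meets it and the baseline value does not meet that same band or threshold. Each subject then appears once per parameter, and baseline ALT 1.5 rising to 8 times ULN is counted in the band above 5 to 10.
3. State that the separate chemistry classes, including Abnormal baseline, are not gated by this baseline condition.

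The cost is a few lines of SAP text and a simpler derivation. No new data are needed and no valid count is given up.

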6.3.3. Analysis Windows and Baseline

The analysis windows around each visit day are provided in [Table 2](#) below.

Table 2: Analysis Windows for Each Scheduled Visit

Scheduled Visit	Analysis Window	
	From	To
Baseline		Before randomization/First Study Treatment
Day 30	Day 1	Day 60
Day 90	Day 61	Day 120
Day 150	Day 121	Day 210
Day 270	Day 211	Day 300
Day 330	Day 301	Day 390
Day 450	Day 391	Day 480
Day 510	Day 481	Day 525
Day 540	Day 526	No upper limit

Data collected at scheduled or unscheduled visits will be used in the analysis if they fall into an analysis window for a scheduled visit. If more than one visit (scheduled or unscheduled) is made

within the window specified above for any scheduled visit, the non-missing assessment closest to the scheduled visit day will be used in the analysis for that visit. However, all data will be included in the subject data listings.

Unless otherwise specified, data collected from assessments that occur more than once prior to initiation of investigational product administration, the latest assessment will be considered the "Baseline" evaluation for analysis.

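### Applied to the creatinine row as a whole, the SAP's no-abnormal-baseline rule leaves a subject who starts and stays above 2 mg/dL uncounted as clinically significant even after a rise of 50% or more (minor)

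*SAP*

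**What the plan says.** The Serum Creatinine row of SAP Appendix 4 has one upper boundary: an increase of at least 50% from baseline, or a value above 2 mg/dL. One asterisk closes the cell, and the footnote says that asterisks mark CS boundaries.

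SAP 6.4.8.2 sets two conditions for every potentially clinically significant (PCS) or CS criterion other than HbA1c. The post-baseline value must meet the threshold, and in addition "Baseline values or any prior post-baseline values do not meet the thresholds listed in Appendix 4". Appendix 4 repeats the second condition: "Baseline values or any previous post-baseline values do not meet the thresholds below". HbA1c is the only parameter set apart ("Hemoglobin A1c criteria is explicitly stated in Appendix 4").

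Protocol 10.4.4.2 has a similar restriction. It plans incidence rates of PCS and CS "values for subjects without PCS/CS value at baseline". SAP Section 8 records that the identification of PCS and CS values was changed from the protocol.

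The same criteria feed the listings: "Separate listings of all subjects with PCS and CS laboratory values will be presented".

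**The concern.** Excluding subjects who are already abnormal at baseline is a sensible, deliberate way to make an absolute cut-off treatment-emergent. It does not suit a limb that is already measured against the subject's own baseline. Joining the two limbs in one row lets the absolute limb switch off the relative one: once baseline exceeds 2 mg/dL the row is met before treatment starts, and a later doubling adds nothing to the count.

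At stake is a by-arm count of marked creatinine rises in the subjects with least renal reserve. ALT, AST and CK have stepped bands, each in its own row, so a subject abnormal at baseline can still be counted on reaching a higher band. Creatinine has no higher band. Two programmers could also produce different CS tables from the same data, because the SAP does not say whether the rule is tested on the row or on each limb.

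**Working it through.** The plan states no count or rate for this criterion, so there is no figure of its own to reproduce. The check runs creatinine courses through the rule.

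**Inputs.** The two limbs come from SAP Appendix 4, the baseline condition from SAP 6.4.8.2 and Appendix 4, 750 subjects per arm from SAP 6.2, and entry at eGFR above 30 mL/min from Protocol 4.2, criterion 5.

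**Rule.** Relative limb: value ÷ baseline ≥ 1.5. Absolute limb: value > 2 mg/dL. Three readings were applied:
- A: whole row; baseline and all prior values must be clear.
- B: whole row, with the or in the condition taken literally; it is enough that baseline or some prior value is clear.
- C: each limb tested separately. No baseline value can be 50% above itself, so the baseline exclusion never touches the relative limb.

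| Course (mg/dL) | Last value against baseline | A | B | C |
|---|---|---|---|---|
| 2.0 → 2.1 | 2.1/2.0 = 1.05 (+5%) | counted | counted | counted |
| 2.0 → 2.0 → 3.0 | 3.0/2.0 = 1.50 (+50%) | counted | counted | counted |
| 2.1 → 2.1 → 3.15 | 3.15/2.1 = 1.50 (+50%) | no | no | counted |
| 2.5 → 5.0 | 5.0/2.5 = 2.00 (+100%) | no | no | counted |
| 2.1 → 1.9 → 3.15 | 3.15/2.1 = 1.50 (+50%) | no | counted | counted |
| 2.1 → 2.2 → 2.3 | 2.3/2.1 = 1.10 (+10%) | no | no | no |

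A subject who starts and stays above 2 mg/dL is left out under both whole-row readings, however large the rise. Testing by limb restores these rises without adding subjects who merely remain above 2 mg/dL (last line).

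**Is creatinine a special case?** Appendix 4 has 4 hematology rows + 5 ALT + 1 alkaline phosphatase + 5 AST + 5 CK + 1 HbA1c + 1 creatinine + 1 bilirubin = 23. Less HbA1c, 22 rows fall under the baseline condition. Creatinine is the only one of the 22 with a change-from-baseline limb. HbA1c also uses change from baseline and is exempt, though its two terms are joined by an and, and the SAP gives no reason for the exemption.

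**Can such subjects enroll?** Protocol 4.2 sets no creatinine limit. The Cockcroft-Gault formula in the notes to SAP Table 3 gives, for an assumed man of 55 years and 85 kg with creatinine 2.1 mg/dL, (140 − 55) × 85 / (72 × 2.1) = 47.8 mL/min. Over assumed ages 45 to 75 and weights 70 to 100 kg, men range from 30.1 to 62.8 and women from 25.6 to 53.4. Many such profiles pass a limit of 30. This is illustrative, because entry uses an eGFR whose formula the documents do not name.

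**Size.** The documents give no share of subjects with baseline above 2 mg/dL. Each 1% is 750 × 0.01 = 7.5 per arm. An assumed 0.5% to 3% gives 3.75 to 22.5 per arm. These are subjects who start above the cut-off, not missed cases. How many stay above it and rise by 50% cannot be derived.

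**The case against.** The strongest reply is that the rule speaks of thresholds, not rows. The creatinine cell holds two, and tested one at a time nothing is lost. Appendix 4 also lists two boundaries in the platelet and white-cell rows, and a strict whole-row test would stop a subject with low baseline platelets from being counted for a very high value, which can hardly be intended. This stands as evidence that the limb reading is open. It does not settle the matter: those boundaries sit in separate lower and upper columns, whereas the creatinine limbs share one cell. The protocol's wording, which removes the subject for the parameter, favours the row reading, but only weakly, since SAP Section 8 says the identification was modified.

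The asterisk could attach only to the 2 mg/dL limb. The 50% rise would then be a PCS criterion, and for every subject a rise that does not cross 2 mg/dL would be absent from the CS outputs. That is a second ambiguity, and the same split of the row would remove it.

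Renal worsening is also looked at elsewhere. The eGFR shift table uses the worst post-baseline value. If eGFR moved as Cockcroft-Gault clearance does, a 1.5-fold creatinine rise would take any baseline below 30 × 1.5 = 45 into the severe category, and a doubling would do so from below 30 × 2 = 60. The cover is partial: the man above would go from 47.8 to 47.8/1.5 = 31.9 and stay moderate. Treatment-emergent adverse events by baseline renal category (SAP 6.4.7) and the acute kidney injury search (Appendix 5) remain, but depend on an event being reported. Percent-change summaries do not count individual crossings. The normal-range shift table "counts the number of subjects with a low, normal or high value at baseline and a low, normal or high value post baseline", so it would show high to high if 2 mg/dL exceeds the upper limit of normal (an assumption; no range is given). As SAP 6.3.3 says of the values not selected for a visit window, "However, all data will be included in the subject data listings", but listings give no by-arm count.

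**Conclusion.** The point holds as a minor weakness in a safety criterion. On the natural whole-row reading, a subject whose creatinine is above 2 mg/dL at baseline and stays above it cannot be counted in the CS table or CS listing for a rise of 50% or more, while a 5% rise from 2.0 to 2.1 mg/dL is counted. This rests on the rule being applied to the row and on both limbs being CS; the SAP confirms neither.

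Three stronger inferences are not supported:
- That every subject who starts above 2 mg/dL is uncountable. With the or taken literally, one who dips to 2 mg/dL or below and then rises is counted.
- That the illustrative 4 to 23 per arm are lost cases. The share is assumed, and the number actually missed may be zero.
- That renal harm would be hidden from the report. The other outputs may show part of it.

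No efficacy analysis or hypothesis test is affected.

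**What to change.** Split the creatinine row in SAP Appendix 4:
- (a) increase of at least 50% from baseline, marked CS and counted in all subjects regardless of baseline level;
- (b) value above 2 mg/dL, marked CS and counted only if baseline is 2 mg/dL or below.

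Report each row and the union, and note the change in SAP Section 8. No new data are needed. The cost is a wording change and one extra table row; counts may be slightly higher.
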